9 INVESTIGATIONAL PLAN

9.1 OVERALL STUDY DESIGN AND PLAN

This double-blind, parallel-group, placebo-controlled, multicenter and multinational study will utilize a dose-finding response adaptive randomization (RAR) design to evaluate the safety, tolerability, and efficacy of BAN2401 in subjects who have MCI due to Alzheimer's disease – intermediate likelihood, or who have mild Alzheimer's disease dementia. The study will take place over approximately 130 months at approximately 125 sites including North America, Europe, and Asia-Pacific countries. (revised per Amendment 08) Approximately 3200 subjects will be screened to provide approximately 800 subjects to receive BAN2401 or matching placebo. Sites in Japan will screen approximately 160 subjects in order to randomize at least 40 Japanese subjects, even if early success is declared or the study achieves 800 subjects randomized. (revised per Amendment 07) An Extension Phase (Part A and Part B) will be implemented to allow for up to 60 months (5 years) of additional treatment. (revised per Amendments 08, 09, 11, 15, and 19)

The present study incorporates a Bayesian RAR design with frequent IA during the Core Study to continually update randomization allocation on the basis of the primary clinical endpoint. (revised per Amendment 01) This approach allows for ongoing assessment of drug futility or evidence for early success and for continued changes in randomization that favor efficacious treatment arms. Thus, the Bayesian approach not only limits exposure of subjects to nonefficacious treatment arms but can also mitigate the risks associated with larger and longer trials required to demonstrate clinical efficacy by leading to more efficient project termination or early advancement to a successful Phase 3 program. In the Core Study, after the 12-month assessments have been completed, treatment will continue to 18 months to follow the time course of any treatment effects observed at 12 months, and to evaluate biomarker and neuroimaging effects that may be consistent with potential disease modification (revised per Amendment 08).

Subjects will be from 2 clinical subgroups, collectively designated as EAD for the purposes of this protocol: (a) MCI due to AD – intermediate likelihood and (b) mild Alzheimer's disease dementia. At study entry, subjects will be stratified according to clinical subgroup, APOE status (*APOE4* positive and negative), and the presence or absence of ongoing AD treatment with AChEIs or memantine or both. (revised per Amendment 01) Randomization into the 2 clinical subgroups (see [Inclusion Criteria, Section 9.3.1](#)) is to remain reasonably balanced whereby at least 60% of the total number of subjects will have MCI due to AD – intermediate likelihood clinical subgroup and at least 30% will have mild Alzheimer's disease dementia. *APOE4* status (positive or negative) must be confirmed for all subjects prior to randomization. (revised per Amendment 05) Subjects who are confirmed *APOE4* positive (*APOE4* hetero- or homozygous) will not be randomized to the 10 mg/kg, biweekly dose. *APOE4* negative subjects will be randomized into 1 of 6 treatment groups ([Table 4](#)), while *APOE4* positive subjects will be randomized into 1 of 5 treatment groups as explained in [Sections 9.4.3](#) (revised per Amendments 04 and 05). Randomization in the Core Study will initially be fixed to each of these dose groups (4:2:2:2:2 ratio, placebo to each of the 5 active treatment arms) (revised per Amendment 08). All study personnel and subjects will be blinded with respect to the dose regimens. After 196 subjects have been randomized into the study, an IA will be conducted and RAR will guide subsequent randomization into dose groups. Interim analyses and RAR will be repeated after 250 subjects have been randomized and again after each

additional 50 subjects until all 800 subjects are randomized, and will then be conducted at 3-month intervals until all subjects complete 12 months of treatment. (revised per Amendment 07) A Bayesian analysis will be conducted at 12 months of treatment to assess for early success, and at 18 months of treatment, regardless of whether early success is achieved at 12 months. (revised per Amendment 09)

Table 4 BAN2401 Dose Regimens – Core Study

Study Arm	BAN2401 Dose (mg/kg)	Infusion frequency
1	Placebo	Biweekly ^a
2	2.5	Biweekly ^a
3	5.0	Biweekly ^a
4	10.0 ^b	Biweekly ^a
5	5.0	4-week intervals ^c
6	10.0	4-week intervals ^c

a: Biweekly = 2-week intervals

b: Subjects who are confirmed *APOE4* positive (*APOE4* hetero- or homozygous) will not be randomized to the 10 mg/kg, biweekly dose. (revised per Amendments 04 and 05)

c: Subjects receiving study drug at 4-week intervals will receive placebo at intervening 2-week time points. (revised per Amendment 04)

Oversight of the IA and RAR will be conducted by an independent Interim Monitoring Committee (IMC). The IMC will consist of 3 members who are external to the company with expertise in Bayesian adaptive design in clinical trials.

The IA and RAR will be conducted by an unblinded external independent data analysis group in accordance with the protocol. This independent group will provide the IA outcomes to the IMC at each interim look. The IMC will ensure the integrity of the IA and response adaptive randomization process through review of primary efficacy data. In addition, the IMC will act in an independent advisory capacity to monitor the Bayesian IA outcomes according to the early success and futility boundaries pre-specified in the protocol. The IMC will inform the sponsor if the boundaries for early success or futility have been crossed. If the study continues to randomize subjects after statistical futility boundary confirmed by the IMC is crossed, it will be considered a failed study. The IMC will not be charged with any subject safety issues, as this will be the responsibility of an independent DSMB. (revised per Amendment 01)

A separate unblinded DSMB will be employed at regular intervals to monitor the overall safety of the Core Study and will make recommendations to the Sponsor as appropriate (revised per Amendments 08 and 11). In addition, the DSMB will meet when a predetermined number of subjects are randomized to assess whether the option for home infusions is feasible during the Core Study (per DSMB charter, if allowed and conducted according to country and local guidelines; home infusions will not be allowed in Germany. (revised per Amendment 14) Upon implementation of Amendment 07, newly enrolled subjects will not be offered the option for home infusions during the Core Study. (revised per Amendment 14) Subjects opting for home

infusions before implementation of Amendment 07 will be allowed to continue with home infusions for the duration of their participation in the Core Study (revised per Amendments 01, 03, 07, and 14). Details regarding DSMB membership and operational characteristics will be provided in the DSMB Charter. The DSMB will be responsible for monitoring the safety of the study only in the Core Study. (revised per Amendment 11)

If the statistical futility boundary as confirmed by the IMC is crossed, the IMC will inform the DSMB. The DSMB will make risk-benefit assessments after reviewing emerging safety and efficacy signals and will provide its recommendations to the sponsor. The sponsor will make the final decision pertaining to study futility after reviewing recommendations by the DSMB. (revised per Amendment 01)

The following estimates are provided:

- The study will end when the last visit for the last subject is concluded.
- The study is planned to begin no later than December 2012 and to end in approximately 2025 or until the drug is commercially available in the country where the subject resides, whichever comes first. (revised per Amendments 07, 08, and 15)
- The maximum estimated period for each subject on study is approximately 86 months. (revised per Amendments 08, 11, and 15)

Administration of BAN2401 to an individual subject may be stopped on the basis of safety-related findings as outlined in [Section 9.3.3](#).

An overview of the study design is presented in [Figure 1](#).

[figure not shown]

Figure 1 Design of Study BAN2401-G000-201

(revised per Amendments 08, 11, 15, and 19)

Subjects not continuing into the Extension Phase Part A will have a follow-up visit 3 months after the last dose of study drug. However, subjects who previously completed the Core Study (through the Follow-Up Visit, Visit 43) at any time before implementation of the Extension Phase Part A, and/or fulfill the Extension Phase Part A inclusion and exclusion criteria, will also be eligible to participate. Subjects in Extension Phase Part A will transition to commercial supplies upon availability for individual subjects at each study site. All subjects ongoing in Extension Part A upon implementation of Protocol Amendment 19 will transition to Extension Part B. Extension Phase Part A and Part B combined will continue for up to 60 months (5 years), or until BAN2401 is commercially available for individual subjects at each study site, at which time the subjects will switch to commercial BAN2401, or in the cases where drug is not yet commercially available, treatment will continue until the benefit to risk ratio from treatment with BAN2401 is no longer considered favorable, whichever comes first. BW = biweekly; M = monthly; IV = intravenous; Q3W = every 3 weeks; Q4W = every 4 weeks; R = randomization.

9.1.1 Prerandomization Phase

The Prerandomization Phase in the Core Study will last for up to 60 days and will include a Screening Period and a Baseline Period. (revised per Amendment 08) The assessments conducted during this phase will include a series of assessments specifically to determine eligibility for randomization into the study. Subjects will be diagnosed according to NIA-AA criteria as either MCI due to AD or mild Alzheimer’s disease dementia as defined by the protocol after completion of MMSE, Wechsler Memory Scale IV-Logical Memory (subscale) I (WMS-IV LMI), Wechsler Memory Scale IV-Logical Memory (subscale) II (WMS-IV LMII), and CDR. Once the diagnosis is made, the WMS-IV LMII inclusion criterion can be applied to all subjects (revised per Amendments 01 and 06). A schematic overview of the process for determining eligibility is shown in [Figure 2](#).

[figure not shown]

Figure 2 Schematic Overview of Eligibility Assessments

CSF = cerebrospinal fluid, MRI = magnetic resonance imaging, PET = positron emission tomography. (revised per Amendment 06)

9.1.1.1 Screening Period

The Screening Visit will occur during the Screening Period, between Day -60 and Day -31. Screening assessments and timing thereof are shown in the Schedule of Screening and Baseline Assessments/Procedures (Table 7).

The purpose of the Screening Period is to obtain informed consent to participate in the study and to establish protocol eligibility. Informed consent will be obtained after the study has been fully explained to each subject and caregiver/informant and before the conduct of any screening procedures or assessments. Procedures to be followed when obtaining informed consent are detailed in Section 5.3. No subject will undergo any further study procedures unless this informed consent has been obtained. All subjects must consent to either a baseline PET scan or a baseline CSF sample to be used to determine study eligibility. Subjects will also be asked to sign separate optional ICFs to enter the CSF and imaging substudies, respectively. For those who consent to both CSF and PET collection for eligibility, samples will be collected as follows:

Subjects in the Core Study whose study eligibility is determined by amyloid PET and who have consented to both substudies will have: (revised per Amendment 08)

- Additional PET scans performed at 12 and 18 months
- CSF samples collected at Baseline, 12, and 18 months.

Subjects whose study eligibility is determined on CSF and who have consented to both substudies will have: (revised per Amendment 08)

- PET scans performed at Baseline, 12, and 18 months
- Additional CSF samples collected at 12 and 18 months

None of the optional consents are required for study eligibility. (revised per Amendment 06)

For the Extension Phase Part A, subjects will need to re consent for the longitudinal amyloid PET substudy before the Extension Screening visit in order to participate. (revised per Amendments 08, 09, 11, and 19)

Consent to blood collection for pharmacogenomic (PG) testing is mandatory for eligibility to enter the study. (revised per Amendment 06)

Study site personnel will interview the subject and caregiver/informant to obtain demographic and clinical information as described in [Section 9.5.1.1](#), and will review inclusion and exclusion criteria as described in [Sections 9.3.1](#) and [9.3.2](#). Prior medications and medications currently being taken by the subject will be reviewed. The Screening Disposition electronic case report form (eCRF) page must be completed to indicate whether the subject is eligible to participate in the study and to provide reasons for screen failure, if applicable.

Subjects who remain eligible for study entry after review of inclusion and exclusion criteria and prior and concomitant medications will then undergo safety assessments. Vital signs will be assessed, height and weight measurements will be taken, and a complete physical examination will be conducted as described in [Section 9.5.1.2](#). Blood will be drawn for a serum pregnancy test in females of childbearing potential only (Section 9.5.1.2), and for clinical laboratory tests in all subjects (Section 9.5.1.2). A urine sample will be collected for drug screening (Section 9.5.1.2). Clinical assessments for eligibility will be conducted during the Screening Visit as described in Section 9.5.1.2. Every effort should be made to conduct these assessments in the morning, but if this is not possible due to the timing of the visit, they should be conducted at the same time of day at all subsequent visits. Testing during the Screening Visit should begin with the clinical assessments in the following order: Mini-mental State Examination (MMSE), Wechsler Memory Scale-IV Logical Memory (subscale) I and II (WMS-IV LMI and LMII), and CDR. The WMS-IV LMII is to be administered 20 to 30 minutes after the completion of LMI. Subject information should be collected in the 20 to 30 minutes between the WMS-IV LM1 and LMII. Subjects who meet criteria for objective memory impairment as determined by the WMS LMII score (See [Inclusion Criteria](#)) will also be evaluated on the Geriatric Depression Scale (GDS) for eligibility. Subjects who meet criteria for the GDS will be administered the Columbia-Suicide Severity Rating Scale (C-SSRS) as a safety assessment ([Section 9.5.1.5](#)), and all remaining Screening Visit assessments will be conducted. The caregiver/informant needs to be present at this visit. (revised per Amendment 01)

Subjects who are eligible following the Screening Visit for eligibility will then undergo noncontrast brain MRI for brain abnormalities that may exclude study participation

(Section 9.5.1.5). The MRI imaging will include fluid attenuating inversion recovery (FLAIR), Gradient Recalled Echo (GRE), T1 and diffusion-weighted sequences to determine the presence of focal lesions that may exclude study participation. An additional scanning sequence will be conducted in all subjects immediately following the safety MRI to obtain vMRI data, as described in Section 9.5.1.3. Results of these MRI assessments will be used as the Baseline Period MRI, against which changes after drug administration will be compared.

9.1.1.2 Baseline Period

Baseline assessments and timing thereof are listed in Table 7 and described in Section 9.5.1.2.

During the Baseline Period, which will extend from Day -30 to Day -1, the subject will return to the study site for additional assessments.

Inclusion/exclusion criteria will again be reviewed, vital signs and weight will be recorded, and a single 12-lead electrocardiogram (ECG) will be conducted. (revised per Amendment 01) A routine physical examination will be conducted and a urine pregnancy test will be conducted for females of childbearing potential. Blood will be collected from all subjects for clinical laboratory tests. The MMSE, the CDR, the ADAS-Cog, and the Functional Assessment Questionnaire (FAQ) will be administered to the subject in the stated order. The caregiver/informant needs to be present at this visit. The C-SRSS will also be administered.

Blood will be collected from all subjects for PG analyses of *APOE4* and blood may be collected for exploratory biomarker analyses as outlined in Appendix 3. (Section 9.5.1.4). (revised per Amendment 01)

Cerebrospinal fluid may be obtained at this visit from subjects who have consented to this procedure, for PK and PD assessments (Section 9.5.1.4, Appendix 3). (revised per Amendment 07)

For further assessment of eligibility, all subjects who pass the preceding screens will then undergo amyloid PET or CSF A β (1-42) assessment (revised per Amendment 06) within 20 days after the Baseline Visit, as an eligibility criterion (Section 9.5.1.2, Section 9.5.1.6). Baseline amyloid PET data will serve as the baseline data for amyloid PET results at 12 and 18 months of treatment for those subjects who consent to be included in the imaging subgroup (total target n=306). The Baseline Visit CSF sample will be used to confirm eligibility and for use as the baseline CSF assessment for those subjects who consent to be included in the CSF substudy. For subjects who screen fail at the Baseline assessment, the Screening Disposition eCRF page must be completed to indicate whether the subject is eligible to participate in the study and to provide reasons for screen failure, if applicable. (revised per Amendments 06 and 07)

Subjects who complete the Baseline Period and meet the criteria for inclusion/exclusion (Section 9.3.1 and Section 9.3.2) will begin the Randomization Phase.

APOE4 status (positive or negative) must be confirmed for all subjects prior to randomization. Subjects who are confirmed *APOE4* positive (*APOE4* hetero- or homozygous) will not be randomized to the 10 mg/kg, biweekly dose. (revised per Amendment 05)

Some subjects who screen fail during the Prerandomization Phase may be eligible for rescreening following sponsor approval. Note that when a subject is rescreened, a new subject number will be issued. All screening and baseline assessments should be repeated *with the following exceptions*:

- **MRI** – No repeat needed if the date of the rescreen is ≤ 90 days from the date of the original screening MRI.
- **Pharmacogenetics** – If a sample was collected, processed, and *APOE4* results issued during the previous screening procedure, another sample is not required to be collected when a subject is rescreened. Great care must be taken to link the APOE status information with the new subject number.
- **PET/CSF** – No repeat needed for eligibility if confirmed amyloid positive (via CSF or PET) during the original screening procedure. If a subject will participate in the longitudinal PET or CSF substudies, quantitative PET or CSF collection should be repeated if the original PET/CSF collection was done >6 months from the date of the original screening procedure. (revised per Amendment 07)

The new subject number will be linked to the initial subject number and the outcomes for procedures that need not be repeated as outlined above. (revised per Amendment 06)

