- e: Amyloid PET should be done at least 10 days before the planned randomization date. For those subjects who consent to CSF and PET eligibility assessments, CSF collection should always precede amyloid PET, and the 2 assessments should be separated by at least 24 hours. For these subjects, a positive amyloid result is needed for only one of the procedures to confirm eligibility (ie, even if one of the 2 results renders the subject ineligible). Subjects who initially consent for only one of the amyloid screening assessments will only be allowed to subsequently consent for the second assessment should the first assessment result be positive. Subjects who consent to Amyloid PET or CSF Amyloid are not required to participate in the respective substudies. For subjects who are approved for rescreening, the amyloid PET need not be repeated for eligibility if confirmed amyloid positive during the original screening procedure. If a rescreened subject will participate in the longitudinal PET substudy, quantitative PET collection should be repeated if the original PET collection was done >6 months from the date of the original screening procedure. (revised per Amendments 06 and 07) .
- f: For subjects who are approved for rescreening, pharmacogenetic testing need not be repeated if a sample was collected, processed, and *APOE4* results issued during the previous screening procedure. Great care must be taken to link the APOE status information with the new subject number.

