- g: For those subjects who consent to the longitudinal CSF substudy, Baseline samples will be used for eligibility assessment and to establish a baseline measure for the longitudinal assessments. CSF should be collected at or after the Baseline Visit, and at least 19 days (21 days for sites in the Asia-Pacific region) before the planned randomization date. For those subjects who consent to both CSF and PET eligibility assessments, CSF collection should always precede amyloid PET, and the 2 assessments should be separated by at least 24 hours. For these subjects, a positive amyloid result is needed for only one of the procedures to confirm eligibility (ie, even if one of the 2 results renders the subject ineligible). For subjects who are approved for rescreening, the CSF need not be repeated for eligibility if confirmed amyloid positive during the original screening procedure. If a rescreened subject will participate in the longitudinal CSF sub-study, quantitative CSF collection should be repeated if the original CSF collection was done > 6 months from the date of the original screening procedure. (revised per Amendments 06 and 07) .

Table 8 Schedule of Procedures/Assessments, Core Study BAN2401-G000-201, Panel A, Visits 3 through 27, Weeks 1 through 49 – Core Study

Phase	Randomization																										
	Treatment																										
Period	3	4	5	6	7	8	9	10	11	12	13	14	15	16	17	18	19	20	21	22	23	24	25	26	27		
Visit ^a	3	4	5	6	7	8	9	10	11	12	13	14	15	16	17	18	19	20	21	22	23	24	25	26	27		
Week	1	3	5	7	9	11	13	15	17	19	21	23	25	27	29	31	33	35	37	39	41	43	45	47	49		
Procedures/ Assessments																											
Vital signs ^d	X	X	X	X	X	X	X	X	X	X	X	X	X	X	X	X	X	X	X	X	X	X	X	X	X		
Weight ^c	X						X							X						X							
Routine physical exam					X					X				X						X							
12-lead ECG					X					X				X						X							
Urine pregnancy test ^f							X							X						X							
Blood for laboratory tests ^g	X	X		X			X			X				X						X							
Urinalysis (revised per Amendment 06)	X	X		X			X			X				X						X							
MMSE ^h							X							X						X							
CDR ^h							X							X						X							
ADAS-Cog ^h							X							X						X							
FAQ ^h							X							X						X							
C-SSRS			X		X		X							X						X							
Safety MRI ⁱ					X		X							X						X							
Volumetric MRI (for PD) ^j					X		X							X						X							
Abbreviated MRI ^k				X																							
Informed consent ^l																											
Amyloid PET ^m																											

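### The rule for repeating the PET/CSF baseline after rescreening counts 6 months from the original screening instead of to the rescreen, so read literally it never triggers for an in-study collection

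*Protocol*

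**What the plan says.** Section 9.1.1.2 tells sites to repeat all screening and baseline assessments when a subject is rescreened, then lists exceptions.

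- **PET/CSF.** No repeat is needed for eligibility if amyloid positivity was confirmed the first time. For a subject entering the longitudinal PET or CSF substudy, the quantitative collection "should be repeated if the original PET/CSF collection was done >6 months from the date of the original screening procedure".
- **Table 7, footnote e (PET).** "quantitative PET collection should be repeated if the original PET collection was done >6 months from the date of the original screening procedure".
- **Table 7, footnote g (CSF).** "quantitative CSF collection should be repeated if the original CSF collection was done > 6 months from the date of the original screening procedure".
- **MRI, in the same list in 9.1.1.2.** "No repeat needed if the date of the rescreen is ≤ 90 days from the date of the original screening MRI".

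On timing, 9.1.1 states: "The Prerandomization Phase in the Core Study will last for up to 60 days and will include a Screening Period and a Baseline Period". Section 9.1.1.2 places the amyloid assessment "within 20 days after the Baseline Visit, as an eligibility criterion". Footnotes e and g add minimum gaps before planned randomization (10 days for PET; 19 days for CSF, or 21 in Asia-Pacific) but no maximum. Inclusion criterion 7 (9.3.1) and 9.5.1.6 bar historical PET scans as substudy baselines.

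**The concern.** The rule is evidently meant to stop an outdated scan or CSF sample from serving as the substudy baseline. What makes a carried-over baseline old is the time from its collection to the rescreen, and that interval does not enter the rule. The MRI exception does use the rescreen date. The PET/CSF wording is the same in all three places, so no passage corrects another.

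The baseline matters because it is one half of two key secondary endpoints in 9.7.1.1: change at 18 months in amyloid PET and in CSF biomarkers. It also enters the exploratory analyses relating amyloid to clinical change (9.7.1.6). MMSE, CDR and ADAS-Cog are not among the exceptions and must be repeated at rescreening, so one subject's clinical and biomarker baselines could come from different dates.

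**Working it through.** **Step 1. Can the trigger be met?** Six months is 365.25 / 2 = about 183 days.

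| Reading of the windows | Largest gap, original screening to original collection |
|---|---|
| Day -60 to Day -1 (Table 7) | 59 days |
| PET at least 10 days before planned randomization (footnote e) | 60 - 10 = about 50 days |
| CSF at least 19 days before planned randomization (footnote g) | 60 - 19 = about 41 days |
| Baseline Visit on Day -1 plus the 20-day allowance (9.1.1.2) | 59 + 20 = 79 days |

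Even the most generous reading is under half of 183 days. No in-study collection can satisfy the condition.

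**Step 2. What would counting to the rescreen do?** Take a PET on day 30 of the first attempt, with months of 30.44 days. As written, the gap is 30 days whenever the rescreen happens. Counted to the rescreen, age = 30.44 x months - 30:

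| Rescreen, months after first screening | Age of PET | Repeat? |
|---|---|---|
| 3 | 61 days | no |
| 6 | 153 days | no |
| 9 | 244 days | yes |
| 12 | 335 days | yes |
| 18 | 518 days | yes |

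**Step 3. Size for one affected subject.** Section 7.2.2.1 gives annual amyloid increases of 2.1% (MCI) and 5.7% (AD). The protocol gives no baseline SUVR, so 1.4 is assumed. A 12-month-old baseline misses:

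- MCI rate: 1.4 x 0.021 = 0.029 SUVR
- AD rate: 1.4 x 0.057 = 0.080 SUVR

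At assumed SUVRs of 1.2 to 1.6 the range is 1.2 x 0.021 = 0.025 to 1.6 x 0.057 = 0.091.

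**Step 4. Size for the PET comparison.** Section 9.7.1.9 uses an SD of 0.4 for change at 18 months, a variance of 0.16. If a share p of subjects (assumed) carries an offset d, the added variance is p(1 - p)d².

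| p | d | Added variance | Relative to 0.16 |
|---|---|---|---|
| 5% | 0.08 | 0.05 x 0.95 x 0.0064 = 0.0003 | 0.2% |
| 20% | 0.08 | 0.20 x 0.80 x 0.0064 = 0.0010 | 0.6% |
| 20% | 0.16 (24 months) | 0.20 x 0.80 x 0.0256 = 0.0041 | 2.6% |

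The last row is a stress case. It raises the standard error by √1.026 - 1 = 1.3%. No equivalent is possible for CSF, because the protocol gives neither a drift rate nor an SD for those markers.

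**The case against.** The intent is clear. A 6-month rule in a list of rescreening exceptions has one sensible meaning, every rescreen needs sponsor approval, and sites may have applied the rule as intended. That stands as a statement about likely practice. It does not rescue the text, which gives the wrong result if followed.

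A historical PET accepted for eligibility could literally be more than 6 months from the original screening, so the condition is not impossible in every case. This is correct but changes nothing, because such a scan is already barred as a substudy baseline.

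Few subjects can be affected. The amyloid assessment follows the other screens, and amyloid-negative failures are outside the exception. What remains are amyloid-positive subjects who failed for another reason, were approved for rescreening more than 6 months after collection, and joined an optional substudy. This stands.

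The Core Study was complete by Amendment 11 (7.1.2.3, 7.2.1.2), and 7.2.1.2 reports amyloid reduction against placebo at P<0.0001 in all dose groups. This also stands: new wording cannot change Core data, and the PET result is not threatened.

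A reader might go further in two ways that the documents do not support:

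- **A 12% to 32% distortion of the endpoint.** Dividing 0.03 to 0.08 by the planned difference of 0.25 SUVR gives those percentages, but it sets one subject's drift against a difference between arm means. It is not a shift in the treatment comparison.
- **Baselines of any age, never repeated.** No numeric cap is written, but enrolment length and sponsor approval limit the age in practice, and the protocol does not show what sites did.

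**Conclusion.** The rule is wrong as written in 9.1.1.2 and in Table 7 footnotes e and g. For an in-study collection the longest possible gap is about 79 days against a trigger of about 183, and no other passage limits the age of a PET or CSF baseline carried over from a first attempt. This part is certain and needs no assumption.

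The consequence is small. It is confined to an uncounted group of rescreened, amyloid-positive substudy subjects. The per-subject PET figure in Step 3 rests on the assumed baseline SUVR, and its upper end applies the AD rate although at least 60% of subjects are to have MCI. Carry-over is settled before allocation, so the expected harm is noise and a misdated change from baseline, with no expected bias between arms. The added variance is probably below 1% for 12-month-old baselines if 5% to 20% of subjects were affected, and those shares are assumptions. The effect on CSF cannot be sized. Severity: minor.

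**What to change.** In 9.1.1.2 and Table 7 footnotes e and g, reword the condition so that the quantitative collection is repeated when the original PET or CSF was obtained more than 6 months before the date of the rescreen. This matches the MRI rule and costs one phrase in three places. It corrects the protocol of record and prevents reuse of the error.

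For the data already collected:

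- Compute baseline age for each substudy subject from the recorded collection and rescreen dates.
- Flag those whose PET or CSF preceded the rescreen by more than 6 months, and report how many there are.
- Run the PET and CSF change-from-baseline analyses without them as a sensitivity analysis.

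This needs no new data. The SAP is not shown and may already provide for such an analysis, in which case only the wording needs correcting.
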